11.2 Adverse Events

Non-serious AEs occurring from the start of study drug administration until EOMS for the subjects in the Main study only or until EOSS for subjects in the Sub-study will be reported in the eCRF. Serious AEs (SAEs) occurring after signing the informed consent form until EOMS for the subjects in the Main study only or until EOSS for subjects in the Sub-study will be reported in the eCRF. All AEs will be coded using MedDRA version 23.1 - September 2020, and classified by SOC and preferred term.

All AEs occurring from the start of study drug administration through the last day of participation in the Main study (EOMS) are considered as TEAEs.

An overall TEAE summary by treatment group will be presented by the number of events and the number and percentage of subjects experiencing one or more events, including all TEAEs, treatment-related TEAEs, treatment-emergent SAEs, severe TEAEs, TEAEs leading to discontinuation, and death.

The number and percent of subjects reporting one or more TEAEs and the number of TEAEs will be tabulated by SOC, preferred term, and treatment group for all TEAEs. Results will be displayed in order of decreasing frequency based on the occurrence rate in the APP13007 group, both across SOC and within each SOC term. Summaries of all ocular TEAEs, ocular TEAEs in the study eye, ocular TEAEs in the non-study eye, all non-ocular TEAEs, TEAEs related to study drug, ocular TEAEs related to study drug in the study eye, non-ocular TEAEs related to study drug, treatment-emergent SAEs, SAEs related to study drug and TEAEs leading to study discontinuation will also be presented in the same manner. The number and percent of subjects reporting one or more TEAEs will also be summarized by maximum severity for all TEAEs, ocular TEAEs in the study eye and non-ocular TEAEs.

The relationship of TEAEs will be determined by the relationship to study drug and/or to the ocular surgical procedure. Ocular TEAEs related to both study drug and surgery or related to surgery only will be summarized separately.

In addition, the incidence of TEAEs occurring in at least 5% of subjects in any treatment group and incidence of non-serious TEAEs above the threshold of 5% of subjects in any treatment group (for data transparency reporting) will be presented.

For summaries by severity of TEAEs, the most severe occurrence for a particular preferred term will be used for a given subject. AEs with missing severity will be considered as ‘Severe’ events for summary purposes, but will be presented as missing in the AE listings.

A TEAE related to study drug is defined as a TEAE with a “Possible”, “Probable” and “Definite” relationship to study drug as defined in [protocol Section 8.3.2](#). These three relationships will be classified as “Related”. For summaries of TEAEs related to study drug, the most related occurrence for a particular preferred term will be used for a given subject. AEs with missing relationship to study drug or surgery will be considered as “Related” for summary purposes, but will be presented as missing in the AE listings.

AEs occurring between EOMS and EOSS for subjects in the Sub-study will be summarized by SOC, preferred term, and treatment group.

All AEs will be listed in a data listing. All SAEs (including SAEs for all subjects who sign the informed consent), AEs leading to study discontinuation, and deaths will be listed separately.

A serious and unexpected suspected adverse reaction (SUSAR) is defined in the [protocol Section 8.2](#). The SUSARs will be summarized and listed.

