8.3.4 Action Taken with Study drug

The action to be taken in response to an AE will be to either discontinue or continue study drug.

Subjects will be permitted to restart study drug if there is a temporary interruption of study drug dosing not more than 1 day due to an AE.

Decrease in the dosing frequency or dosing duration of the study drug is not allowed in this study.

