9.5.2 Management

Investigator will use clinical judgment to determine the appropriate IOP-lowering medication to use and when to withdraw study drug and procedures, in consultation with the Study Medical Monitor.

It is important to note that prostaglandin-based IOP lowering medications are prohibited in this study.

- After randomization and start of study drug, if a subject has an IOP > 30 mmHg the Investigator may commence non-prostaglandin-based IOP-lowering medication while continuing the study drug, with appropriate follow-up at the next planned visit or at an unscheduled visit. The subject may require assessment at an unscheduled visit at the investigator's discretion.
 - If the IOP is < 30 mmHg at the next visit, the subject may continue on study drug.
 - If at the next visit, the IOP remains > 30 mmHg while on IOP-lowering medication, then the study drug may be discontinued and alternative IOP-lowering medication

may be started, after consultation with the Study Medical Monitor. The subject should continue in the study and complete the assessments indicated in Table 1 through Visit 6 (POD22) (Main Study) or Visit 7 (POD85) (Endothelial Cell Sub-study). The Study Medical Monitor should discuss the persistent elevation of IOP with the Sponsor Medical Monitor.

- After randomization and start of study drug, an IOP of ≥ 21 mmHg AND an increase > 10 mmHg from the Visit 2 (POD1)/pre-dose baseline (both criteria must be met) is considered clinically significant and the Investigator should consider starting non-prostaglandin-based IOP-lowering medication while continuing the study drug, with appropriate follow-up at the next planned visit or at an unscheduled visit.
 - If the IOP reduction is satisfactory at the next visit, the subject may continue on study drug.
 - If the IOP reduction of IOP is not satisfactory at the next visit, then the study drug may be discontinued and alternative IOP-lowering medication may be started, after consultation with the Study Medical Monitor. The subject should continue in the study and complete the assessments indicated in Table 1 through Visit 6 (POD22) (Main Study) or Visit 7 (POD85) (Endothelial Cell Sub-study). The Study Medical Monitor should discuss the persistent elevation of IOP with the Sponsor Medical Monitor.

Medications used for treating increased IOP will be recorded in the Concomitant Medications section of the eCRF, noting that they were used to reduce IOP.

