10.3.3 Analysis of Safety

Analysis of safety data will be performed for all subjects in the Safety Population.

Adverse events will be coded using Medical Dictionary for Regulatory Activities (MedDRA) and classified by system organ class and preferred terms. Adverse events will be summarized by total number of TEAEs, number of subjects reporting TEAEs, ocular TEAEs (affecting the study eye and/or the non-study eye and/or both eyes, when appropriate), non-ocular TEAEs, SAEs, serious and unexpected suspected adverse reactions (SUSARs), discontinuing study drug due to an AE, by relationship to study drug and/or ocular surgical procedure, and by severity.

The IOP data for both eyes will be summarized at screening, Visit 6 (POD22)/Early Termination (Withdrawal) visit and change from screening. The observed IOP data and change-from-baseline (POD1) for the study eye will be summarized at each post-surgery visit.

The data for slit lamp biomicroscopy examination endpoints will be summarized at each visit. The summary of change-from-baseline at each post-surgery visit will be presented for the study eye.

Dilated indirect ophthalmoscopic examination findings for the study and non-study eye will be summarized at screening and Visit 6 (POD22)/Early Termination (Withdrawal).

Visual Acuity data will be summarized at each visit. The summary of change-from-baseline at each post-surgery visit will be presented for the study eye.

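### SAP 11.2 tabulates and lists AEs leading to study discontinuation, but specifies no table or listing of AEs leading to study drug discontinuation, the category protocol 10.3.3 names

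*SAP*

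**What the plan says.** Protocol 10.3.3 lists the categories by which AEs will be summarised. One of them is "discontinuing study drug due to an AE, by relationship to study drug and/or ocular surgical procedure, and by severity". The category concerns study drug, not study participation.

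SAP 11.2 has three outputs that bear on this:

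- The overall TEAE summary has rows that include "severe TEAEs, TEAEs leading to discontinuation, and death". The discontinuation row does not say what is discontinued.
- Among the tables by system organ class and preferred term: "TEAEs leading to study discontinuation will also be presented in the same manner".
- Among the listings: "AEs leading to study discontinuation, and deaths will be listed separately".

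On drug stopping, protocol 8.3.4 says: "The action to be taken in response to an AE will be to either discontinue or continue study drug". Protocol 9.5.2 covers raised IOP. If at the next visit "the IOP remains > 30 mmHg while on IOP-lowering medication, then the study drug may be discontinued", after consultation with the Study Medical Monitor. It then adds: "The subject should continue in the study and complete the assessments indicated in Table 1", to Visit 6 in the Main Study or Visit 7 in the Endothelial Cell Sub-study. A parallel rule with the same follow-up applies to the second IOP criterion (at least 21 mmHg with a rise of more than 10 mmHg from pre-dose baseline). Protocol 8.1.1 makes both IOP criteria reportable AEs.

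**The concern.** Stopping the drug and leaving the study are separate events in these documents. Protocol 6.3 lets the investigator discontinue a subject from either. SAP 7.1 tabulates them separately: study discontinuation in the ITT population and early drug discontinuation in the Safety population. A programmer who follows SAP 11.2 as written will therefore select subjects who left the study.

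Protocol 9.5.2 creates a group for whom the two differ: drug stopped because of an AE, subject retained. IOP increase is the first corticosteroid-class ocular risk listed in protocol 1.5.1.4. A reader of the report would expect to see, by arm, which AE terms ended treatment. The specified table and listing would omit these subjects, and the overall row would include or omit them depending on how it was programmed.

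**Working it through.** The check is mainly a comparison of text. The plan states no figure to reproduce.

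**Step 1. What each output captures for a subject whose drug is stopped under protocol 9.5.2 and who completes follow-up.**

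| Output | IOP event shown? | Drug stop shown? | Linked? |
|---|---|---|---|
| SAP 11.2 table, TEAEs leading to study discontinuation | No | No | No |
| SAP 11.2 listing, AEs leading to study discontinuation | No | No | No |
| SAP 11.2 overall row, TEAEs leading to discontinuation | Count only, if read as drug | Count only, if read as drug | No AE term |
| SAP 11.2 all-TEAE and study-eye ocular tables | Yes | No | No |
| SAP 11.2 all-AE listing | Yes | Not specified | Not specified |
| SAP 11.3.1 summary and listing of IOP threshold exceedances | Yes | No | No |
| SAP 7.1 drug discontinuation before 14 days, by reason and arm | No AE term | Yes | No |

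No specified table gives the AE term together with the drug stop.

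**Step 2. How wide the group is.**

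- Under the 9.5.2 steps, IOP-lowering medication is started at one visit, and the drug may be stopped if the response is inadequate at the next. Dosing ends on POD14. Among scheduled visits, only POD4 followed by POD8 allows this while dosing is still under way. Unscheduled visits or investigator judgement could add cases.
- Some other AE-related stops coincide with leaving the study. A subject who asks to stop drug is withdrawn (protocol 6.3), and one stopped for a deleterious effect may be (9.1.1.3). The existing table can capture those.
- Rescued subjects also stop drug and stay, but rescue itself is not an AE (protocol 8.1.1), so they do not enter this category on that ground.

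**Step 3. Size per subject.** The documents give no rate of drug discontinuation for IOP. With about 185 subjects planned per arm (protocol 10.4), each affected subject is 1/185 = 0.5% of an arm. As an illustration with assumed counts only, 1 to 4 such subjects in one arm would be 1/185 = 0.5% to 4/185 = 2.2%. The study-discontinuation table would show none of them. SAP 7.1 would count all of them as drug stops, without the AE term.

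**The case against.** The best case for the SAP has four parts.

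- **Protocol 10.3.3 asks only for a summary.** It does not require a table by preferred term or a listing for this category. If the overall row is read as drug discontinuation, the commitment is met. This stands in part: the conflict with the protocol depends on an undefined row, and the missing table and listing are supporting outputs. But the only two outputs in SAP 11.2 that name what is discontinued both name the study, so the favourable reading cannot be assumed.
- **Nothing is hidden.** A reader might infer that raised IOP is left out of the safety report. The documents do not support that. The events appear in the all-TEAE, ocular and maximum-severity tables, in the related-TEAE tables if judged related, in the all-AE listing and in the IOP threshold outputs. The drug stops are counted by arm in SAP 7.1. This objection stands in full.
- **The importance is easily overstated.** A reader might take this as loss of a dose-limiting tolerability measure, or of the event most likely to separate the arms. Neither description is in the documents. The trial tests one fixed regimen with no dose modification, and the risk mitigation table (protocol Table 2) reports no clinically meaningful drug-related IOP elevation in the toxicology studies or in CPN-201.
- **The group is small.** The restrictions in step 2 support this, although no count can be given.

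**Conclusion.** The point holds in a limited form. SAP 11.2 does not clearly deliver the drug-discontinuation summary in protocol 10.3.3, and gives no reason for using study discontinuation instead. Subjects whose drug is stopped for an IOP AE and who stay in follow-up under protocol 9.5.2 are absent from the preferred-term table and from the separate listing. The loss is the tabulated link by arm between AE term and drug stop, not the events or the stops themselves. For these subjects the two outputs can only under-count AE-related drug stops. The number is likely small and cannot be estimated from the documents.

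This conclusion assumes that the outputs are programmed as worded and that such subjects remain in the study as 9.5.2 directs. No efficacy result or listed safety endpoint changes. It is worth correcting because it is a plain mismatch between protocol and SAP in a standard safety output.

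**What to change.** In SAP 11.2:

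1. Define the overall row as TEAEs leading to discontinuation of study drug, and add a separate row for TEAEs leading to study discontinuation.
2. Add a table by system organ class and preferred term, by arm, and a listing, of TEAEs leading to discontinuation of study drug. Derive both from the action taken with study drug in protocol 8.3.4.
3. Keep the existing study-discontinuation table and listing. Replacing them would lose AEs that led to withdrawal after dosing had ended.

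The cost is SAP wording, one extra table and one extra listing. This assumes that the action taken is captured for each AE in the eCRF. Protocol 8.3.4 defines the possible actions but does not show the field, so confirm this before amending. If it is captured, no new data are needed.

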11.3 Other Safety Endpoints

The ophthalmic assessments for safety include IOP measurement using Goldmann applanation tonometry, ETDRS assessment of best corrected visual acuity by the Pinhole method, Slit Lamp biomicroscopy assessment of the relevant signs of inflammation, and dilated indirect ophthalmoscopy assessment. The safety assessments will be collected up to EOMS (POD22 or Early Termination before POD22).

11.3.1 Intraocular Pressure

IOP assessments will be performed from Screening through EOMS for the study eye. IOP assessments will be performed at Screening and EOMS for the non-study eye.

For the study eye, the IOP data and change from baseline (POD1 pre-dose) at each post-surgery scheduled visit through EOMS will be summarized by treatment group using descriptive statistics, including 95% CI for the mean of change from baseline. The IOP change from Screening to each scheduled post-surgery visit through EOMS for the study eye will be summarized to evaluate any potential impact from IOP lowering medication use on the surgery day (Day 0). A box and whisker plot will be presented for the IOP change from baseline through EOMS and for the IOP change from Screening through EOMS for the study eye. The IOP change from POD15 to POD22 for non-rescued subjects who complete the study will be summarized for the study eye.

The IOP increase from baseline and increase from Screening will be categorized as ≤ 0 , 1-5, 6-10, >10 (mmHg). The number and percentage of subjects in each category will be tabulated at each post-surgery visit for the study eye. In addition, subjects with an IOP ≥ 21 mmHg and an increase > 10 mmHg from baseline, and subjects with an IOP > 30 mmHg at any time following initiation of study drug will be summarized and listed for the study eye.

The IOP data collected after taking rescue medication will be excluded from the summary tables and plots for the study eye.

The IOP data at Screening and EOMS, and change from Screening to EOMS for the non-study eye will be summarized using descriptive statistics.

All IOP data, including data collected after taking rescue medication, will be presented in a data listing.

11.3.2 Best Corrected Visual Acuity

Since the BCVA endpoint will also be assessed for efficacy, this endpoint has been described in the [Section 10.2.1](#). The assessments for the study eye will be performed from Screening through EOMS for safety evaluation. The assessment for the non-study eye will be performed at Screening and EOMS.

The BCVA LogMAR scores and change from baseline (POD1 pre-dose) will be summarized descriptively by treatment group at each post-surgery scheduled visit through EOMS for the study eye. The BCVA base LogMAR scores change from baseline will be classified as ≤ 0 , $0 < - < 0.2$ and ≥ 0.2 , which are equivalent to ≤ 0 line (visual acuity improved), $0 < - < 2$ lines, and ≥ 2 lines (visual acuity worsened). The number and percentage of subjects in each category will be tabulated at each post-surgery scheduled visit for the study eye.

The BCVA LogMAR scores collected after taking rescue medication will be excluded from the summary tables for the study eye.

The BCVA LogMAR scores at Screening and EOMS, and change from Screening to EOMS for the non-study eye will be summarized using descriptive statistics.

All BCVA data, including data collected after taking rescue medication, will be presented in a listing.

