7.3.1.2 ETDRS Best Corrected Visual Acuity Measurement by Pinhole Method

Best corrected visual acuity measurement will be performed using the ETDRS eye chart at a preferred (but not required) distance of 4 meters. The testing should be conducted under standardized lighting conditions using the pinhole method for the study visits indicated in Table 1. Other testing distances may be used as long as it is consistent with the recommendations provided for the ETDRS chart being used and will be used consistently at each visit.

The subject starts at the top of the chart and reads down until the subject reaches a row where the subject is unable to correctly read any letters on that line.

The ETDRS Acuity Log Score was calculated as follows:

1. Determine the last row where the subject can correctly identify at least one (1) letter in that row. This is the Base Logarithm of the Minimum Angle of Resolution (logMAR) line.
2. Determine the log score for the Base logMAR line.
3. Add 0.02 (T=0.02) log units for every letter that is incorrectly identified up to and including the Base logMAR line.

The results will be recorded in the source documentation and the eCRF.

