9.1.2 Study Termination

- The study can be stopped at any time if deemed necessary by the Sponsor Medical Monitor, in consultation with the Study Medical Monitor, due to safety concerns. Safety will be monitored on an ongoing basis via periodic masked review of AEs and other safety endpoints.
 - If it is observed that visual acuity worsens by 2 lines (Base LogMAR change of 0.2 using ETDRS chart) at Visit 6 (POD22) in the treated study eye as compared to Visit 2 (POD1), in 6 consecutive subjects, no further doses of study drug will be administered to any subjects in the study until a

comprehensive evaluation can be performed, and, if possible, a cause is identified.

- Safety assessments will be performed throughout the course of the study. The APP13007 Investigator's Brochure, Section 1.4.1 and the Risk Mitigation plan in Table 2 provide guidance for the Investigator on potential anticipated AEs that may occur. Any potential important safety issues that arise will be reviewed by the Study Medical Monitor, in consultation with the Sponsor Medical Monitor, to identify the appropriate course of action.
- If the Sponsor elects to terminate the study for any reason, the Investigator will be responsible for notification of the IRB and will withhold further dosing of study drug.

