10.2 Analyses of Secondary Efficacy Endpoints

10.2.1 Secondary Efficacy Endpoints

The secondary efficacy endpoints are:

- Proportion of subjects with ACC count = 0 (ACC grade = 0) at PODs 4, 8 and 15
- Proportion of subjects with Ocular Pain grade = 0 at PODs 4, 8 and 15
- Proportion of subjects with ACF grade = 0 at POD8 maintained through POD15
- Proportion of subjects with ACF grade = 0 at PODs 4, 8 and 15
- Mean change from baseline in ACC grade at PODs 4, 8, and 15
- Mean change-from baseline in Ocular Pain grade at PODs 4, 8 and 15
- Mean change from baseline in ACF grade on PODs 4, 8 and 15
- Number of subjects rescued on or prior to each visit and overall
- Mean change from baseline in best corrected visual acuity (BCVA) by pinhole method using an ETDRS chart at PODs 4, 8 and 15

The ACC count and Ocular Pain grade will be graded using the same grading scale described for primary efficacy endpoints ([Section 10.1.1](#)).

The ACF will be graded as follow:

Grade	Description
0	None
1	Faint
2	Moderate (iris and lens details clear)
3	Marked (iris and lens details hazy)
4	Intense (fibrin or plastic aqueous)

Subjects who meet the rescue criteria may be rescued and placed on an appropriate alternative therapy as determined by the Investigator. The rescue criteria are provided in the [protocol Section 9.4](#).

The ETDRS visual acuity (logMAR score) will be calculated as follows using Original EDTRS Chart 1 and Chart 2:

1. Determine the last row where the subject can correctly identify at least one (1) letter in that row. This is the base logMAR line.
2. Determine the log score for the base logMAR line.
3. Add 0.02 ($T = 0.02$) log units for every letter that is incorrectly identified up to and including the base logMAR line.

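### SAP 11.3.2 sorts visual-acuity change by whole-row base LogMAR, which is coarser than the letter score already derived, and its lowest category labels unchanged eyes as improved (minor)

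*SAP*

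**What the plan says.** Protocol 7.3.1.2 and SAP 10.2.1 give the same three-step scoring. Step 1 reads: "Determine the last row where the subject can correctly identify at least one (1) letter in that row". Step 2 takes the log value of that row, the base line. Step 3 adds 0.02 "log units for every letter that is incorrectly identified up to and including the base logMAR line". Testing starts at the top of the chart, and the subject "reads down until the subject reaches a row where the subject is unable to correctly read any letters on that line".

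SAP 11.3.2 uses both quantities. It first summarises LogMAR scores and their change from POD1 pre-dose at each post-surgery visit. It then changes measure for the categories: "The BCVA base LogMAR scores change from baseline will be classified as" ≤ 0, above 0 but below 0.2, and ≥ 0.2. The lowest category is described as ≤ 0 "line (visual acuity improved" and the highest as ≥ 2 "lines (visual acuity worsened".

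The study-level rule in protocol 9.1.2 uses the same measure and cut-point. It refers to the case where "visual acuity worsens by 2 lines (Base LogMAR change of 0.2 using ETDRS chart", comparing Visit 6 with Visit 2 in six consecutive subjects. The list of changes in SAP Amendment 1 records that the use of the base score in 11.3.2 was clarified.

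**The concern.** Base LogMAR stops before step 3 of the documents' own score. It ignores every letter missed on the rows down to the base line, and a single letter read or missed at the bottom can move it a whole line. The finer score is already derived for the efficacy analysis of covariance and for the safety means, so the coarser one is not forced by the data.

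The table is the only count of visual-acuity losses in SAP 11.3.2. Extra scoring noise in such a count adds apparent losses and hides some real ones in both arms, which tends to blur a between-arm difference. Visual acuity is a named safety endpoint, so the count should be as sharp as the data allow.

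The wording of the lowest category is a second, separate matter. A reader of the finished table would take the percentage in the ≤ 0 row as the percentage improved, although it includes every eye with no change.

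**Working it through.** **Chart arithmetic.** SAP 11.3.2 and protocol 9.1.2 equate 0.2 logMAR with 2 lines, so one line is 0.2 / 2 = 0.1. At 0.02 per letter, a row has 0.1 / 0.02 = 5 letters, and 2 lines are 10 letters. The plan's equivalence reproduces exactly.

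**Can the two scores disagree?** Score = base + 0.02 × letters missed down to the base row. In each constructed pair below, at least one letter is read on every row down to the base, so the stopping rule is met.

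| Pair | POD1 | Later visit | Base change | Score change |
|---|---|---|---|---|
| A | Base 0.1, none missed: 0.10 | 2/5 on 0.3, 1/5 on 0.2, 1/5 on 0.1: 0.10 + 0.02 × (3+4+4) = 0.32 | 0 (≤ 0) | +0.22, 11 letters |
| B | Base 0.2, none missed: 0.20 | Base 0.3, 4 missed on 0.4 and 4 on 0.3: 0.30 + 0.16 = 0.46 | +0.1 (middle) | +0.26, 13 letters |
| C | Base 0.2, 3 missed on 0.3 and 4 on 0.2: 0.20 + 0.14 = 0.34 | Base 0.4, none missed: 0.40 | +0.2 (worsened) | +0.06, 3 letters |

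A and B are letter-scored losses of more than 2 lines that miss the top category. C is a 3-letter loss that enters it.

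**The label.** A change of exactly 0 satisfies ≤ 0 on either score. The cut-point produces the error, so changing the score would not remove it.

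**How often?** The documents give no test-retest data, so this part is illustration only. All inputs are assumed: 5 letters per row, a logistic reading curve with scale 0.03–0.08 logMAR, guessing 0–10%, baseline thresholds uniform on 0.1–0.5 logMAR, and stopping at the first row with no letter read. Ranges run over nine combinations of curve and guessing rate.

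| True loss | Quantity | Base LogMAR | Letter score |
|---|---|---|---|
| 0 | SD of change | 0.07–0.20 | 0.035–0.08 |
| 0 | Flagged ≥ 0.2 | about 1–20% | under 1% |
| 0.2 | Flagged ≥ 0.2 | about 61–80% | about 55–62% |
| 0.3 | Not flagged | about 1–21% | about 0–8% |

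The SD of change for base is about 1.9 to 3 times that of the letter score. At a true loss of 0.2 the base score flags more eyes. That loss lies on the cut-point, so the share flagged is one half plus half the share landing exactly on it. For base, 22–59% of eyes land on the true change, which gives 0.5 + 0.22/2 = 0.61 to 0.5 + 0.59/2 = 0.795. The finer score has fewer such ties.

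**The case against.** The strongest reply is that the choice is deliberate and consistent. Protocol 9.1.2 measures a 2-line loss on base LogMAR, SAP 11.3.2 follows it, and the amendment record shows the point was considered. That stands. A reader might infer that the SAP contradicts the protocol or that the two need reconciling; they already agree. Replacing the base table outright would create a mismatch that does not exist now.

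A reader might also infer that base LogMAR simply hides losses. It does not do so uniformly: at a true loss of 0.2 it flags more eyes than the letter score. Losses are missed or falsely flagged only if the letter score is taken as the reference. That is reasonable, since it is the documents' own full score, but it is a choice.

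The frequencies can be challenged too. The 20% needs both the shallowest curve and 10% guessing; with no guessing the range at zero change is 0.7–9.5%. Baseline is the day after surgery, when recovery is the more natural expectation, and with a true 0.1 improvement base flags 0–9%. Pair A's pattern (base change ≤ 0 with a letter-scored loss ≥ 0.2) is uncommon: 0.03–2.4% of eyes at a true 0.2 loss and 0–5.3% at 0.3.

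Finally, letter-scored information is reported elsewhere: the descriptive change in 11.3.2, the analysis of covariance at PODs 4, 8 and 15 (SAP 10.2.2.2), and the listing. Protocol 7.3.1.1 also makes any clinically relevant deterioration in a clinical finding an adverse event. This limits the consequence, although means can conceal a few large losses and a listing is not a count by arm.

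**Conclusion.** The point holds as a minor one, in two separate parts. First, the change categories rest on a coarser and noisier measure than one the SAP already derives, and the scoring rules show that the two can disagree in both directions. Second, describing ≤ 0 as improved is a label error whichever score is used; it should not be attributed to base LogMAR, although whole-row scoring makes exact ties more common.

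The disagreement follows from the documents alone. Its frequency does not: every percentage above rests on assumed reading curves, guessing rates and true changes. The table is descriptive, carries no specified test and affects no primary analysis. In a masked randomised comparison the scoring noise should dilute a difference and not favour an arm.

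**What to change.** In SAP 11.3.2:

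- Keep the base-LogMAR table, so that a display aligned with protocol 9.1.2 remains.
- Add the same table on change in the full letter-scored LogMAR, as the main display of visual-acuity loss. Here ≥ 0.2 means a loss of 10 letters or more.
- In both tables, split ≤ 0 into < 0 (improved) and 0 (no change).
- Add a footnote defining the two scores and saying that their ≥ 2-line counts may differ.

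The rule in protocol 9.1.2 is not touched. The cost is SAP wording, one extra table shell and the explanation of two counts. No new data are needed.
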